2.3 Treatment Assignment and Blinding

In Induction Period 1, approximately 966 subjects will be randomized in a 2:1 ratio to risankizumab 1200 mg IV dose or placebo. The randomization at baseline will be stratified by number of prior failed biologics (0, 1 vs > 1), baseline steroid use (yes vs no), and baseline Adapted Mayo score (≤ 7 vs > 7).

In Induction Period 2, subjects who do not achieve clinical response and received IV risankizumab in Induction Period 1 will be randomized 1:1:1 to risankizumab 1200 mg IV, 360 mg SC and 180 mg SC groups. The randomization will be stratified by number of prior failed biologics (0, 1 vs > 1), baseline steroid use (yes vs no), and baseline Adapted Mayo score (≤ 7 vs > 7). Subjects who do not achieve clinical response and received placebo in Induction Period 1 will receive risankizumab 1200 mg IV.

2.4 Sample Size Determination

In Induction Period 1, approximately 966 subjects will be randomized to the risankizumab 1200 mg IV dose or placebo in a randomization ratio of 2:1. The sample size for this study is based on the expected proportion of subjects who achieve clinical remission per Adapted Mayo Score at Week 12. The sample size has been re-assessed after analyzing combined PK, safety and efficacy results from Sub-Study 1. It is determined to provide adequate power for the primary endpoint and selected ranked secondary endpoints and adequate responders to meet the sample size requirement for Study M16-066. Assuming clinical remission rate of 6% in the placebo arm and 16% of the risankizumab treatment arm at Week 12, a sample size of 644:322 subjects in risankizumab 1200 mg IV dose and placebo group will provide at least 90% power to detect the 10% treatment difference in clinical remission rate between the risankizumab dose and placebo using two-sided

Miettinen and Nurminen test at a 0.05 significant level. The assumed remission rates were based on Sub-Study 1 for bio -IR population and on ustekinumab data for non-bio-IR population. The same sample size will also provide at least 90% power for ranked secondary endpoints, clinical remission per full mayo score at Week 12, endoscopic response at Week 12, endoscopic remission at Week 12, clinical response per adapted mayo score at Week 12 and clinical response per partial adapted mayo score at Week 4.

3.0 Endpoints

Below are the endpoint definitions for efficacy variables:

- Mayo Score
 - Full Mayo Score: composite score of UC disease activity based on the
 - stool frequency subscore [SFS] (0 – 3), rectal bleeding subscore [RBS] (0 – 3), physician's global assessment [PGA] subscore (0 – 3) and endoscopic subscore (0 – 3). The endoscopic subscore will be based on central readings after adjudication (when applicable). The Full Mayo score ranges from 0 – 12 points with higher scores representing more severe disease.
 - Partial Mayo Score: Full Mayo score excluding the endoscopic subscore.
 - Adapted Mayo Score: Full Mayo score excluding the PGA subscore.
 - Partial Adapted Mayo Score: Adapted Mayo score excluding the endoscopic subscore.
- Clinical Remission per Adapted Mayo: stool frequency subscore (SFS) ≤ 1 , and not greater than baseline, rectal bleeding subscore (RBS) = 0, and endoscopic subscore ≤ 1 without the evidence of friability
- Clinical Response per Adapted Mayo: decrease from Baseline ≥ 2 points and $\geq 30\%$, PLUS a decrease in RBS ≥ 1 or an absolute RBS ≤ 1
- Clinical Response per Partial Adapted Mayo (without endoscopy): decrease from Baseline ≥ 1 points and $\geq 30\%$, PLUS a decrease in RBS ≥ 1 or an absolute RBS ≤ 1
- Clinical Remission per Full Mayo: Full Mayo score ≤ 2 with no subscore > 1

- Endoscopic Improvement: endoscopy subscore of 0 or 1 without the evidence of friability
- Endoscopic Remission: endoscopic subscore = 0
- Histologic Remission: Geboes score of < 2.0
- Histologic Endoscopic Mucosal Improvement (HEMI): Endoscopic subscore of 0 or 1 without the evidence of friability and Geboes score \leq 3.1.
- Histologic Endoscopic Mucosal Remission (HEMR): Endoscopy subscore of 0 and Geboes score < 2.0

Note: Evidence of friability during endoscopy in subjects with otherwise "mild" endoscopic activity will confer an endoscopic subscore of 2.

3.1 Primary Endpoint(s)

The primary efficacy endpoint is the achievement of clinical remission per Adapted Mayo score at Week 12.

3.2 Secondary Endpoint(s)

Secondary endpoints are:

1. The achievement of clinical response per Adapted Mayo score at Week 12
2. The achievement of endoscopic improvement at Week 12
3. The achievement of histologic endoscopic mucosal improvement (HEMI) at Week 12
4. The achievement of endoscopic remission at Week 12
5. The achievement of clinical response per Partial Adapted Mayo score at Week 4
6. The achievement of no bowel urgency at Week 12
7. The achievement of no abdominal pain at Week 12
8. The achievement of histologic endoscopic mucosal remission (HEMR) at Week 12

9. Change from Baseline to Week 12 in Functional Assessment of Chronic Illness Therapy-Fatigue (FACIT-Fatigue)
10. Change from Baseline to Week 12 in Inflammatory Bowel Disease Questionnaire (IBDQ) total score
11. Occurrence of UC-related hospitalizations through Week 12
12. The achievement of no nocturnal bowel movements at Week 12
13. The achievement of no tenesmus at Week 12
14. Change from Baseline to Week 12 in number of fecal incontinence episodes per week
15. Change from Baseline to Week 12 in number of days per week with sleep interrupted due to UC symptoms

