5.2.1 Inclusion Criteria

1. Males or females \geq 18 and \leq 80 years of age, or minimum age of adult consent according to local regulations at the Baseline Visit. Sub-Study 2 only: Where locally permissible, subjects 16 to $<$ 18 years of age who meet the definition of Tanner Stage 5 for development (refer to Appendix G) at the Baseline Visit.
2. Confirmed diagnosis of UC for at least 3 months prior to Baseline. Appropriate documentation of biopsy results consistent with the diagnosis of UC or in the assessment of the Investigator, must be available.
3. Active UC with an Adapted Mayo score of 5 to 9 points and endoscopic subscore of 2 to 3 (confirmed by central review).
4. Demonstrated intolerance or inadequate response to one or more of the following categories of drugs: aminosalicylates, oral locally acting steroids, systemic steroids (prednisone or equivalent), immunomodulators, and/or biologic therapies
 - Demonstration of intolerance requires no minimum dose or duration of use.
 - Inadequate response is defined as outlined below:
 - Oral aminosalicylates (e.g., mesalamine, sulfasalazine, olsalazine, balsalazide):
 - Signs and symptoms of persistently active disease, in the opinion of the Investigator, during a current or prior course of at least 4 weeks of

treatment with 2.4 g/day mesalamine (2 g/day if controlled release), 4 g/day sulfasalazine, 1 g/day olsalazine, or 6.75 g/day balsalazide,

- Oral locally acting steroids (e.g., budesonide, beclomethasone):
 - Signs and symptoms of persistently active disease in the opinion of the Investigator, during or after a course of at least 4 weeks of treatment with 9 mg/day budesonide or 5 mg/day beclomethasone,
or
 - Inability to taper oral budesonide to at or below 6 mg/day without recurrent active disease,
- IV or Oral systemic steroids (prednisone or equivalent):
 - Signs and symptoms of persistently active disease in the opinion of the Investigator, during or after tapering of at least one regimen consisting of a dose equivalent to prednisone \geq 40 mg/day orally for 3 weeks or intravenously for 1 week,
or
 - Inability to taper oral systemic steroids at or below a dose equivalent to prednisone 10 mg/day without recurrent active disease,
- Immunomodulators:
 - Signs and symptoms of persistently active disease in the opinion of the Investigator, during a current or prior course of at least 90 days of treatment with one or more of the following:

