- For each binary secondary endpoint except for UC-related hospitalization, the estimand is the difference in the proportion of subjects achieving the endpoint regardless of premature discontinuation of study drug and without initiation or dose escalation of UC-related corticosteroids and without UC-related surgery (ileostomy, colectomy, or proctocolectomy) (see Section 8.0) between risankizumab 1200 mg IV and placebo in the ITT2 population.
- For occurrence of UC-related hospitalization, the estimand is the difference in the proportion of subjects having UC-related hospitalization through Week 12 regardless of premature discontinuation of study drug and regardless of initiation or dose escalation of UC-related corticosteroids or UC-related surgery (ileostomy, colectomy, or proctocolectomy) (See Section 8.0) between risankizumab 1200 mg IV and placebo in the ITT2 population.
- For each continuous secondary endpoint, the estimand is the difference in the mean change from baseline of the endpoint regardless of premature discontinuation of study drug and without initiation or dose escalation of UC-related corticosteroids and without UC-related surgery (ileostomy, colectomy, or proctocolectomy) (See Section 8.0) between risankizumab 1200 mg IV and placebo in the ITT2 population.

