3.3 Additional Efficacy Endpoint(s)

The primary and secondary efficacy endpoints are listed in Section 3.1 and Section 3.2, respectively. The additional efficacy endpoints are:

Induction Period 1

- The achievement of SFS = 0, RBS = 0, and endoscopic subscore = 0 at Week 12
- The achievement of SFS \leq 1 at Week 4, Week 8, Week 12 respectively
- The achievement of RBS = 0 at Week 4, Week 8, Week 12 respectively
- The achievement of clinical response per Partial Adapted Mayo score at Week 8, Week 12 respectively
- Change from Baseline in Partial Adapted Mayo score at Week 4, Week 8, Week 12 respectively
- Change from Baseline to Week 12 in Full Mayo score
- Change from Baseline in SFS at Week 4, Week 8, Week 12 respectively
- Change from Baseline in RBS at Week 4, Week 8, Week 12 respectively

- Change from Baseline in hs-CRP at Week 4, Week 8, Week 12 respectively
- Change from Baseline in FCP at Week 4, Week 12 respectively
- Change from Baseline to Week 12 in UCEIS
- The achievement of histologic remission at Week 12
- Change from Baseline to Week 12 in European Quality of Life 5 Dimensions (EQ-5D-5L)
- Change from Baseline to Week 12 in Work Productivity and Impairment Questionnaire – UC (WPAI-UC)
- Change from Baseline to Week 12 in UC-SQ
- The achievement of IBDQ remission (IBDQ total score ≥ 170) at Week 12
- The achievement of IBDQ response (increase of IBDQ ≥ 16 from Baseline) at Week 12
- Time to clinical response per Partial Adapted Mayo
- Change from baseline in PGIS at Week 4, Week 8, Week 12 respectively
- PGIC at Week 4, Week 8, Week 12 respectively
- Occurrence of UC-related surgeries through Week 12
- The achievement of clinical response per Adapted Mayo score at Week 12 in subjects with pancolitis at Baseline
- Change from Baseline to Week 12 in Short Form-36 (SF-36)
- The achievement of clinical remission per Full Mayo score at Week 12 in subjects with a Full Mayo score of 6 to 12 at Baseline

Induction Period 2

- The achievement of clinical remission per Adapted Mayo at Week 24
- The achievement of clinical remission per Full Mayo score at Week 24 in subjects with a Full Mayo score of 6 to 12 at Baseline
- The achievement of clinical response per Adapted Mayo score at Week 24
- The achievement of no abdominal pain at Week 24
- The achievement of no bowel urgency at Week 24
- The achievement of endoscopic remission at Week 24

- The achievement of endoscopic improvement at Week 24

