4.0 Analysis Populations

The following population sets will be used for the statistical analyses:

Intent-to-Treat Population

Sub-Study 2 Induction Period 1:

ITT2 includes all randomized subjects who received at least one dose of study drug during Induction Period 1. The **ITT2** will be used for all efficacy analysis, and demographic and baseline characteristics summary for Induction Period 1. Subjects will be included in the analysis according to the treatment groups that they are randomized to.

Sub-Study 2 Induction Period 2:

ITT2_P2 includes all subjects who received at least one dose of risankizumab during Induction Period 2 from Sub-Study 2. Subjects will be included in the analysis according to the treatment groups that they are re-randomized to the Induction Period 2 and the subjects who received placebo induction treatment during 12-Week Induction Period 1 and entered the Induction Period 2 will be also included (denoted as placebo/risankizumab). This analysis population will be used for efficacy analysis in Induction Period 2.

Safety Analysis Set

The safety analysis will be based on the corresponding safety analysis sets. Subjects will be analyzed in a treatment group based on the actual treatment received.

Sub-Study 2 – Induction Period 1

SA2 consists of all subjects who received at least one dose of study drug during Induction Period 1 in Sub-Study 2.

Sub-Study 2 Induction Period 2:

SA2_P2 consists of all subjects who received at least one dose of risankizumab during the Induction Period 2 after Week 12 in Sub-Study 2.

All Risankizumab:

SA2_ALL includes all subjects who received at least one dose of risankizumab any time during the Sub-Study 2.

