9.0 Efficacy Analyses

9.1 General Considerations

All efficacy analyses will be conducted based on ITT2 for Induction Period 1. The overall type I error rate of the primary and secondary endpoints will be strongly controlled using a graphical multiple-testing procedure¹ as described in Section 13.0. Analyses for the efficacy endpoints in Induction Period 2 will be performed based on ITT2_P2.

The primary analysis will be performed after all ongoing subjects have completed the Sub-Study 2 activities up to Week 24 and the Sub-Study 2 database has been locked. This will be the only and final analysis for the primary and secondary efficacy endpoints as well as all additional efficacy endpoints in Sub-Study 2. Treatment assignments will be unblinded to AbbVie for statistical analyses.

Unless otherwise specified, categorical variables will be analyzed using Cochran-Mantel-Haenszel (CMH) test for common risk difference, stratified by Advanced Therapies-IR status (yes vs no), baseline steroid use (yes vs no), and baseline Adapted Mayo score (≤ 7 vs > 7). If there is a stratum for a treatment group that has no subject in it, a value of 0.1 will be added to all cells in the corresponding table in order to prevent dividing by 0, as suggested in Greenland and Robins (1985).³ Greenland and Robins (1985)³ variance estimator is used for the common risk difference. For all stratification factors (including the randomization stratification factors) used for CMH analyses, their values will be based

on actual values. Continuous variables collected longitudinally (more than one post baseline visits) will be analyzed using Mixed-Effect Model Repeat Measurement (MMRM) method. Continuous variables collected with only one post baseline visit will be analyzed using Analysis of Covariance (ANCOVA) model. For multi-level categorical endpoints PGIC, percentage of each outcome category will be reported descriptively, and no statistical comparison will be performed. For time to event analysis, Kaplan-Meier method will be used. For all stratification factors (including the randomization stratification factors) used for analyses, their values will be based on actual values.

Baseline refers to the last non-missing observation on or before the first administration of study drug in Induction Period 1 or randomization if no study drug is given.

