UC-related hospitalizations through Week 12	Risankizumab 1200 mg IV vs. placebo	Occurrence of UC-related hospitalization through Week 12	ITT2	IE1: premature discontinuation of study drug IE2: initiation or dose escalation of UC-related corticosteroids IE3: occurrence of the UC-related surgery (ileostomy, colectomy, or proctocolectomy) All data after IE1 will be used. All data after IE2 or IE3 will be used.	Proportion of subjects having at least one UC-related hospitalization through Week 12

The binary secondary endpoints will be analyzed based on ITT2 using the same approach as that for primary endpoint as specified in Section 9.3.2. Specifically, CMH adjusting for stratification factors will be used to construct the treatment difference, the associated

95% CI and p-value between risankizumab 1200 mg IV group and placebo group. The NRI-MI will be the primary approach for missing data handling in the analyses of binary secondary efficacy endpoints except for Occurrence of UC-related hospitalization, of which AO data will be used.

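### The four symptom-absence endpoints (6, 7, 12, 13) are tested without adjusting for whether the subject had the symptom at Baseline: a valid test that gives up precision and is hard to read

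*SAP*

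**What the plan says.** SAP (Sub-Study 2) 3.2 lists endpoint 6 as "The achievement of no bowel urgency at Week 12". Endpoints 7, 12 and 13 have the same form, and none has a Baseline condition. The entry rule in Protocol 5.2.1 is "Active UC with an Adapted Mayo score of 5 to 9 points and endoscopic subscore of 2 to 3"; no criterion asks for urgency, abdominal pain, nocturnal stools or tenesmus.

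SAP 9.4.2 states: "The binary secondary endpoints will be analyzed based on ITT2 using the same approach as that for primary endpoint". SAP 4.0 says that ITT2 "will be used for all efficacy analysis, and demographic and baseline characteristics summary for Induction Period 1". For binary secondary endpoints other than hospitalization, SAP 2.1 says "the estimand is the difference in the proportion of subjects achieving the endpoint". Under SAP 9.1 the CMH test is "stratified by Advanced Therapies-IR status (yes vs no), baseline steroid use (yes vs no), and baseline Adapted Mayo score", cut at 7.

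Protocol 5.3.1.1 has the electronic diary handed out at Screening, and Protocol 10.3 lists all four symptoms among its daily items. SAP 7.1 does not include them in the Baseline summary. SAP 9.3 to 9.6 plan no analysis in subjects who had the symptom at Baseline. SAP 13.0 places endpoints 6 and 7 among the first ten secondary endpoints, and 12 and 13 in the Holm group.

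**The concern.** A subject without urgency at Baseline and still without it at Week 12 counts as having achieved endpoint 6. For a symptom diary item, the Baseline value is likely to be among the strongest predictors of the Week 12 value. Leaving it out of the strata gives up precision on four endpoints inside the type I error family. It also means that the reported percentage cannot be read as the share of affected patients who lost the symptom, and no planned table lets a reader separate the two groups.

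Elsewhere the plan does use Baseline values of the outcome. The models for continuous endpoints in SAP 9.2.2 adjust for the Baseline measurement. The imputation model in SAP 9.2.1 includes it for binary endpoints and gives no bowel urgency as an example of one imputed directly.

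**Working it through.** **The plan's own figure.** SAP 2.4 claims at least 90% power for the primary endpoint (6% vs 16%, 644:322, two-sided 0.05). Pooled rate = (322 × 0.06 + 644 × 0.16)/966 = 0.1267; null SE = 0.0227; alternative SE = 0.0196; (0.10 − 1.96 × 0.0227)/0.0196 = 2.83, so power is 99.8%. The claim holds. The same section also claims 90% power for some secondary endpoints, but for none of 6, 7, 12 or 13, so there is no stated figure to contradict.

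**Inputs for the symptom endpoints.** The arm sizes 644 and 322 come from SAP 2.4. The rest are assumptions:
- b = share symptom-free at Baseline: 10%, 20% or 30%
- q = share of those symptom-free at Week 12: 75% in both arms
- symptomatic subjects symptom-free at Week 12: 35% vs 20%

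**Formulas.**
- ITT2 rates: p1 = bq + (1−b) × 0.35 and p0 = bq + (1−b) × 0.20
- Unstratified variance: Vu = p1(1−p1)/644 + p0(1−p0)/322
- Variance with the Baseline symptom stratum: Vs = (1−b)[0.35 × 0.65/644 + 0.20 × 0.80/322] + b × 0.75 × 0.25 × (1/644 + 1/322)
- Approximate power: Φ(z − 1.96)

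At b = 20%: p1 = 0.15 + 0.28 = 0.43 and p0 = 0.15 + 0.16 = 0.31. Vu = 0.2451/644 + 0.2139/322 = 0.001045. Vs = 0.8 × 0.000850 + 0.2 × 0.000873 = 0.000855. The ratio is 0.82; z = 0.12/√Vu = 3.7 and 0.12/√Vs = 4.1.

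| b | ITT2 rates | Difference | Vs/Vu | z unstratified → stratified | Power |
|---|---|---|---|---|---|
| 10% | 39.0% vs 25.5% | 13.5 points | 0.89 | 4.4 → 4.6 | 99.2% → 99.6% |
| 20% | 43.0% vs 31.0% | 12.0 points | 0.82 | 3.7 → 4.1 | 96.0% → 98.4% |
| 30% | 47.0% vs 36.5% | 10.5 points | 0.775 | 3.2 → 3.6 | 88% → 95% |

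The variance cut is therefore about 11%, 18% and 22.5%. The stratum recovers precision; it does not change the ITT2 difference. The 15-point difference among symptomatic subjects appears only in an analysis limited to them (z = 4.6 at b = 20%).

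**A smaller effect.** With 30% vs 20% in symptomatic subjects and q = 90%, power without and with the stratum is 80.8% and 89.6% at b = 10%, 67.3% and 83.6% at b = 20%, and 54.0% and 75.2% at b = 30%. The first of each pair uses the pooled-null formula and the second the unpooled one, which accounts for about 1 point of each gap (92.3% vs 93.6% at b = 0).

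**Type I error.** With no treatment effect, b = 20% and q = 90%, an unstratified test rejects in 5.0% of simulated trials. With the SAP's rule of adding 0.1 to each cell where an arm is empty, simulated error was 5.4% to 6.3% with the planned 8 strata and 4.8% to 6.5% with 16. The added stratum makes no material difference.

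**Where dilution vanishes.** If the drug also keeps symptom-free subjects free (75% vs 60%), the ITT2 difference is (1−b) × 15 + b × 15 = 15 points at any b.

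**The case against.** The best defence is that nothing here is wrong. The proportion symptom-free at Week 12 among all randomized and dosed subjects is a coherent estimand, and staying symptom-free despite active disease is something a drug can influence. Any dilution pulls towards no difference, so it cannot create a false claim. Under the 35% vs 20% assumptions, power as planned is already 96% at 20% symptom-free. The variance comparison is against an unstratified test, while the plan already stratifies on three factors, so the true gain may be smaller. All of this stands, and it is why the point is an improvement and not a correction.

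A second defence is sparse data. At 10% symptom-free, about 32 placebo subjects would spread over 8 new strata, about 4 each. This does not stand as a reason to refuse: SAP 9.1 already has a rule for empty strata, and the simulated error with 16 strata was about the same as with 8.

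A reader might also cite Full Mayo remission, assessed "in subjects with a Full Mayo score of 6 to 12 at Baseline", as proof that the plan removes Baseline achievers elsewhere. It does not show that. Full Mayo remission allows no subscore above 1, and entry requires an endoscopic subscore of 2 or 3, so no eligible subject is in remission at Baseline. The limit concerns severity.

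**Conclusion.** The point holds as a cheap improvement. Endpoints 6, 7, 12 and 13 are tested without using a Baseline value that the trial collects. This costs precision and leaves the response rates hard to interpret. The variance cut of about 11% to 22.5% depends on the assumed Baseline symptom-free share, on equal Week 12 rates in those subjects, and on an unstratified comparator. The documents give no symptom-free share. Protocol 3.0 calls urgency and tenesmus hallmark symptoms, which suggests few symptom-free subjects for endpoints 6 and 13; it says nothing similar of abdominal pain or nocturnal stools.

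Three stronger readings are not supported:
- A reader might infer that these endpoints fail to measure achievement. The estimand in SAP 2.1 is clear and the randomized comparison is sound.
- A reader might take dilution of the effect as established. It requires little or no drug effect in symptom-free subjects, and its size requires a share that the documents do not give.
- A reader might extend the point to stand-alone SFS ≤ 1, RBS = 0 and IBDQ remission. These lie outside type I error control (SAP 13.0), and SAP 3.3 already sets them beside change from Baseline in SFS and RBS, or IBDQ response. No change is needed there.

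**What to change.** Keep ITT2 as the analysis population and leave the test family and its order alone. For endpoints 6, 7, 12 and 13 only:

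1. Add Baseline presence of that symptom (yes/no) as a CMH stratum.
2. Write down the diary rule for each symptom (window, number of days, minimum entries) and apply the same rule at Baseline and Week 12. Neither document defines it. The general Baseline definition in SAP 9.1, the last non-missing observation, would otherwise rest on a single diary day.
3. Tabulate Baseline status of each symptom by arm with the characteristics in SAP 7.1.
4. Add a supplementary rate and difference in subjects who had the symptom at Baseline, outside the test family.

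The cost is SAP wording and programming before unblinding; no new data are needed. The downsides are up to 16 strata instead of 8, some of them sparse and covered by the existing rule for empty strata, and a smaller sample in the supplementary display.
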